9.4.7 Adverse Event Follow-up

Patients with radiographic disease progression will be followed every 3 months by telephone until the study is completed (last patient, last death in the study). Follow-up telephone calls will ascertain vital status, possible occurrence of second malignancies, and subsequent treatment as outlined in [Section 5.7](#). In the event of death, attempts will be made to establish the date and cause of death, as applicable.

9.4.8 Medical Events of Interest

Selected non-serious AEs are classified as MEOIs (see below) and must be recorded as such on the AE Case Report Forms and reported the Sponsor either by electronic media or paper on a MEOI Report Form. Sponsor Contact information can be found in [Section 9.4.6](#).

MEOIs for this trial include the following:

- DLTs
- An overdose of Sponsor's product that is not associated with clinical symptoms or abnormal laboratory results.
- An elevated AST or ALT lab value that is $\geq 3x$ ULN and an elevated total bilirubin lab value $\geq 2x$ ULN and, at the same time, an alkaline phosphatase laboratory value that is $< 2x$ ULN, as determined by way of protocol-specified laboratory testing or unscheduled laboratory testing.

***Note:** These criteria are based upon available regulatory guidance documents. The purpose of the criteria is to specify a threshold of abnormal hepatic tests that may require an additional evaluation for an underlying etiology. The trial site guidance for assessment and follow up of these criteria can be found in the Investigator Trial File Binder (or equivalent).

- The following confirmed treatment-emergent autoimmune conditions:
 - Pneumonitis
 - Hypoxia or dyspnea \geq Grade 3
 - Colitis
 - Endocrinopathies: diabetes mellitus, pancreatitis, or adrenal insufficiency
 - Vasculitis
 - Hepatitis
 - Transaminitis: \geq Grade 2 (AST or ALT $> 3x$ ULN and bilirubin $> 2x$ ULN) OR AST/ALT $> 10x$ ULN
 - Systemic lupus erythematosus
 - Guillain-Barre syndrome
 - Skin reactions: vitiligo, pemphigoid
 - Events suggestive of hypersensitivity, cytokine release, influenza-like illness, systemic inflammatory response syndrome (SIRS), or infusion reaction syndrome.

Subjects should be assessed for possible MEOIs prior to each dose of study treatment. Lab results should be evaluated and subjects should be asked for signs and symptoms suggestive of an immune-related event. Subjects who develop an MEOI thought to be immune-related should have additional testing to rule out other etiologic causes. If lab results or symptoms indicate

possible immune-related MEOIs, then additional testing should be performed to rule out other etiologic causes. If no other cause is found, then it is assumed to be immune-related.

MEOIs identified from the date of first dose through 90 days following cessation of treatment, or 30 days after the initiation of a new anticancer therapy, whichever is earlier, need to be reported to the Sponsor within 24 hours of the event in the same manner as outlined for SAEs (Section 9.4.6).

9.4.9 Pregnancy

Several nonclinical studies have already demonstrated that the PD-L1/PD-1 signaling pathway is essential in establishing maternal/fetal tolerance, which is necessary for embryo-fetal survival during gestation.³¹ As a result, no developmental or reproductive toxicity studies have been conducted with atezolizumab. The effects of atezolizumab on human reproduction or on the fetus or the developing infant are unknown but it is expected to have an adverse effect. Furthermore, it is not known whether atezolizumab is excreted in human milk; however, antibodies are known to cross the placenta and are excreted in breast milk during lactation.

Based on the critical role that PD-L1/PD-1 pathway plays in the maintenance of maternal-fetal tolerance and the excretion of antibodies during lactation, atezolizumab should not be administered to pregnant women or nursing mothers. The effects of atezolizumab on human reproduction or on the fetus or the developing infant are unknown but it is expected to have an adverse effect.

Absence of pregnancy must be confirmed prior to initiation of atezolizumab. Female patients of childbearing potential should utilize contraception and take active measures to avoid pregnancy while undergoing atezolizumab treatment and for at least 90 days after the last dose of atezolizumab.

If a female patient inadvertently becomes pregnant while on treatment with CMB305 or atezolizumab, they will be immediately removed from the study. The site will contact the patient at least monthly to document the patient's status until the pregnancy has been completed or terminated. The outcome of the pregnancy will be reported to the Sponsor without delay and within 24 hours if the outcome is an SAE (e.g., death, abortion, congenital anomaly, or other disabling or life-threatening complication to the mother or newborn). The study investigator should make every effort to obtain permission to follow the outcome of the pregnancy and report the condition of the fetus or newborn to the Sponsor. If a male patient impregnates his female partner, the study personnel at the site must be informed immediately and the pregnancy reported to the Sponsor.

Sexually active men and FCBPs must use an effective method of birth control during the course of the study, in a manner such that risk of failure is minimized. Before enrolling FCBP in this clinical trial, all FCBPs must be advised of the importance of avoiding pregnancy during trial participation and the potential risk factors for an unintentional pregnancy. All patients (men and women) must sign an informed consent form documenting this discussion.

All FCBPs must have a negative pregnancy test within 2 weeks prior to the study regimen initiation. If the pregnancy test is positive, the patient must not be enrolled in the study.

In addition, all FCBPs should be instructed to contact the Investigator immediately if they suspect they might be pregnant (e.g., missed or late menstrual period) at any time during study participation.

If, following initiation of study dosing, it is subsequently discovered that a trial patient is pregnant or may have been pregnant within one month before or 4 months after study regimens, the patient will be permanently discontinued. The patient will be followed for as long as possible by the Investigator or designated health care professional to determine pregnancy outcomes for both mother and child. If the female partner of a male patient enrolled in the study becomes pregnant, the Investigator (or designated health professional) should request permission to approach the partner regarding follow-up in order to determine pregnancy outcomes of the mother and baby.

9.4.10 Laboratory Safety Assessments

Blood will be collected a specific study visits as outlined in [Section 8.2](#) and the schedules of events for each treatment arm. Laboratory assessments to be performed include, but are not limited to, the following:

- Hematology: white blood cell (WBC) count with differential, ANC, red blood cell (RBC) count, Hb, hematocrit, platelet count, PT/PTT, and INR;
- Clinical chemistry (or local panel if inclusive of the following): sodium, chloride, potassium, glucose, blood urea nitrogen (BUN), creatinine, calcium, AST, ALT, total bilirubin, alkaline phosphatase, lactic acid dehydrogenase, total protein, and albumin; and
- Urinalysis (at baseline): protein, glucose, blood, leukocytes, nitrites, urobilinogen, bilirubin, pH, specific gravity, and ketones.

Screening safety laboratory safety assessments should be performed within 4 days of treatment initial. On dosing days, hematology and clinical chemistry assessments should be performed and reviewed prior to study drug administrations. These assessments may be done up to 48 hours prior to dosing.

Results will be documented in the patient CRFs. Clinically significant findings may be recorded as AEs.

9.4.10.1 Thyroid Function Tests

Assessments for thyroid function including triiodothyronine [T_3], thyroxine [T_4], and thyroid stimulating hormone [TSH] will be performed at screening and at least every 3 months while being treated with atezolizumab. Patients will be monitored for changes in thyroid function during treatment with atezolizumab for clinical signs and symptoms of thyroid disorders. Assessments will be performed at the start of treatment, periodically during treatment, and as indicated based on clinical evaluation. Results will be documented in the patient CRFs. Clinically significant findings may be recorded as AEs.

9.4.11 Other Laboratory Tests

Blood samples will also be obtained for immunological testing and serology for atezolizumab concentration. Testing for HIV, HepB, and HepC will be performed at screening and must be negative for entry into the study. Blood for immunological testing will be drawn twice at baseline to ensure a good yield. Results will be documented in the patient CRFs. Clinically significant findings may be recorded as AEs.

LV305 was originally derived from HIV, but most of the genome has been replaced to enhance safety and specificity. The product utilizes 3rd generation lentiviral vector technology, which means that it is devoid of all HIV-derived accessory genes.⁷ However, some proteins are included in the particle that may cause screening tests for HIV to become positive as a result of the treatments, although confirmatory testing would likely be considered indeterminate. The conventional screening test for HIV infection is the repeatedly reactive immunoassay (IA), followed by a confirmatory test. If a patient is tested for HIV and screened positive, the CDC recommends further testing with an FDA-approved 2nd generation antibody immunoassay to detect HIV-1 and/or HIV-2 antibodies.³² This test would usually be interpreted as positive if bands appear at the site of two or more of the following HIV antigens: p24, gp41, or gp120/160. If only one band is positive, the test would be considered indeterminate. Specimens that are reactive on the initial assay and negative or indeterminate on the HIV-1/HIV-2 antibody differentiation IA are then to be tested with an FDA-approved nucleic acid test (NAT) for HIV-1 RNA. Under normal circumstances, a reactive NAT result indicates the presence of acute HIV-1 infection and a negative result indicates the absence of HIV-1 infection. However, at least one NAT (the Roche COBAS AmpliPrep/COBAS Taq-Man HIV-1 Test, v2.0) was reported to have been falsely positive in two patients who had been treated with a different lentivirus.³³ An extensive search failed to detect wild-type infectious HIV-1 or vector-derived replication-competent virus and a PCR assay for HIV proviral DNA (Roche COBAS AMPLICOR HIV-1

MONITOR Test, v1.5), as well as a p24 enzyme-linked immunosorbent assay (ELISA), were both negative. Unfortunately, there is no simple path to a definitive diagnosis. While there is a chance of seroconversion, it is predicted to be low because the lentiviral vector used in this program is replication-incompetent and integration-deficient. Even if seroconversion occurs in some assays, it does not mean that the patient has HIV (unless they had become truly infected from some other exposure); careful follow-up testing needs to be done to evaluate that potential. Testing will be done at study entry and on Day 168 to evaluate the chance of seroconversion with LV305; any positives will be further evaluated to determine the true status of infection. Patients are also given a 'Dear Doctor' letter at study entry in case they have HIV testing done at an external lab.

9.4.12 Vital Signs

Vital sign assessments performed at specified study visits will include temperature, HR, and resting BP. These assessments should be performed prior to dosing and 30 minutes postdose administration on drug dosing days. For the first atezolizumab infusion, the patient's vital signs (HR, respiratory rate, BP, and temperature) should be measured within 15 minute of the infusion, during the 60-minute infusion (every 15 [\pm 5] minutes), and 30 minutes after the infusion. For subsequent infusions, vital signs do not need to be obtained during the infusion if the prior infusion was tolerated without symptoms.

9.4.13 Physical Examination

A complete physical examination including height and weight will be performed during screening. Subsequent physical examinations will be simple symptom-directed examinations. Clinically significant deteriorations will be recorded as AEs.

9.4.14 12-Lead Electrocardiogram (ECG)

A 12-lead ECG will be done at screening and at the final post-treatment Visit (Day 105). Clinically significant findings may be recorded as AEs.

9.4.15 LV305 Persistence

For subjects treated with CMB305, peripheral blood will be collected to assay for the persistence of LV305 at baseline, and 6, 12, and 24 months by PCR. Depending on the results through 12 months, annual assessments may continue until 2 consecutive samples show no evidence of LV305 persistence.

10.0 STATISTICAL CONSIDERATIONS

10.1 Study Endpoints

The study endpoints ([Section 4.2](#)) include both clinical efficacy and safety. Where possible, parameters will be quantified for direct comparisons between the treatment groups.

10.2 Data Analysis

The final analysis will be conducted when at least 72 deaths have been observed, or sooner if the Sponsor so decides. Details of all analyses, populations, and data handling rules will be provided in a Statistical Analysis Plan (SAP) and finalized prior to database lock.

10.2.1 Analysis Populations

For the purpose of statistical analysis, there are 2 analysis populations: Intent-to-Treat population (ITT), and Safety population.

The ITT population consists of all randomized subjects. All analyses of this population will be based on the treatment arm to which the subjects are randomized.

The Safety Population will consist of all patients who received at least one injection/dose of study treatment. The Safety Population is the primary population for safety analyses including AEs and clinical laboratory data. Trial product exposure will also be summarized using the Safety Population.

10.2.2 Analyses

In general, categorical variables will be summarized by number and percentages and continuous variables will be summarized with descriptive statistics. All study data will be provided in listings.

10.2.2.1 Patient Disposition

Summaries will include patients who completed the study and for those who did not complete the study, reasons for early discontinuation.

10.2.2.2 Baseline Characteristics

Patient age, race, gender, weight, height, and other demographic information including medical history, disease history, and medication history will be summarized by treatment group.

10.2.2.3 Treatment Administration/Compliance

Treatment administration, exposure, and compliance with study treatments/procedures will be documented and summarized. Exposure and compliance data will be summarized for all patients in each treatment group/arm.

10.2.2.4 Efficacy Analyses

10.2.2.4.1 Primary Efficacy Analysis

The primary efficacy analysis will be the evaluation of OS and PFS based on the ITT Population.

Overall survival is defined as the time interval from randomization to death of any cause. Patients who are alive will be censored at the last known date alive or data analysis cutoff date, whichever is earlier. PFS is defined as the time interval from randomization to tumor progression or death. Accordingly, the precise definition of progression and the timing of imaging scans to progression are very important. Every effort must be made to assure that timeframes for follow-up imaging scans are achieved, so that both treatment groups can be usefully compared. Assessments must be adequate to evaluate target lesions, non-target lesions, and to search for new lesions.

PFS will be based on RECIST 1.1 response guidelines modified to use irRC-specific confirmation. PFS will be defined as the time from randomization to disease progression or death (any cause), whichever occurs first. The irRC modification requires a confirmation of progressive disease (PD) at least 4 weeks later with imaging; once confirmed, the date of progression is defined as the first date that the total tumor burden was shown to have increased by at least 20% compared with the nadir. Patients who do not have disease progression or have not died will be censored at the date when the last tumor assessment determines a lack of progression. If a patient begins a new anti-cancer therapy or has radiotherapy or surgery at a lesion site prior to confirmed progression (or death), the patient will be censored at the last assessment where the patient was documented as progression free prior to the intervention. Patients with two or more missing response assessments prior to a visit with progression (or death) will be censored at the last visit where the patient is documented to be progression free.

The primary efficacy analysis will be the evaluation of OS and PFS using Kaplan-Meier methodology and will be performed on the ITT Population for each treatment arm. Kaplan-Meier plots and 95% confidence intervals (CIs) for 75%, 50% and 25% survival, if reached, will be provided for each treatment group.

10.2.2.4.2 Secondary Efficacy Analysis

A secondary efficacy analysis will be based on the proportion of patients that are progression-free at 6 months after start of study drug treatment (Day 0). Each treatment group will be evaluated with a Simon 2-stage design (Section 10.3.1). Time-to-next-treatment and DMFS will be compared between treatment arms based on a stratified log-rank test. The Kaplan-Meier curve will summarize TTNT graphically by treatment arm. Tabular summaries of the Kaplan-Meier curves will be provided by treatment arm.

Immune response and histologic and molecular tissue changes in tumor tissue or peripheral blood will be summarized by treatment arm.

10.2.2.5 Safety

Descriptive statistics will be performed for all safety information including AEs, SAEs, laboratory findings and discontinuations of patients at all data collection timepoints. No formal statistical hypothesis will be tested.

The highest toxicity grades per patient will be tabulated for AEs and laboratory measurements, and the number and percent of patients reporting AEs (all, severe or worse, serious and related) will be quantified. Listings will be required for all on-study deaths, SAEs and AEs that lead to withdrawal from study. New SAEs experienced by patients during the Screening Period (pre-study treatment) will be reported to IMDZ if the events are considered related to study procedures and will be tabulated separately.

10.2.2.6 Exploratory

10.2.2.6.1 Overall Survival and Progression-Free Survival

Exploratory comparisons between treatment arms of OS and PFS will be based on stratified log-rank tests. Weighted log-rank tests will be explored if delayed treatment effect is observed.

Exploratory analyses of OS at 6, 12, 18, and 24 months, and PFS at 3 and 12 months will also be assessed.

10.2.2.6.2 Overall Response Rate and Duration of Response

Overall response rate is defined as the number of patients with best overall response of CR or PR divided by the number of evaluable patients.

Duration of response is defined as the time from CR or PR to progression or death, among patients with CR or PR. The DOR event and censoring rules are the same as that described

under PFS. Exploratory comparisons of the DOR will be based on stratified log-rank tests. ORR will be compared between treatment arms using a stratified logistic regression model. TGR, PAR, CBR, and quality of life will be evaluated for each group.

10.2.2.6.3 Immunogenicity

Descriptive statistics will be performed comparing the baseline and treatment administration peripheral blood NY-ESO-1-responsive T cells between the 2 treatment arms. Analyses will be performed to determine if there are any statistically significant changes from baseline values. Changes from baseline in serial anti-NY-ESO-1 antibodies will be expressed as geometric mean titers.

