4.1.3 Exploratory Objectives

The exploratory objectives are the following:

- To compare efficacy assessments, such as tumor growth rate (TGR), and progression arrest rate (PAR)
- To compare PFS and OS²⁸ between treatment arms
- To evaluate the immunogenicity of CMB305 in combination with atezolizumab compared to atezolizumab alone
- To evaluate available pre-, on-, and post-treatment tumor tissue and blood for histologic, immunohistologic, and genomic markers
- To evaluate the best overall response rate (ORR; by Response Evaluation Criteria in Solid Tumors [RECIST] v1.1 modified to use immune-related Response Criteria [irRC]²⁷) and duration of response (DOR)
- To evaluate the clinical benefit rate (CBR)

- To evaluate the quality of life as a composite endpoint including but not limited to the following: while on study, the incidence of hospitalization, transfusions, and laboratory markers (eg. absolute neutrophil count, hemoglobin and platelets)

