10.2.2.6.4 Biomarkers

Descriptive statistics will be provided for biomarkers and treatments will be compared using analysis of variance (ANOVA), or non-parametric method when appropriate, of specific genes (e.g., T-cell receptors) and/or gene-networks (e.g., signaling of immune cells) and gene modules (e.g., sets of genes [typically 100-200]) that are up- or down-regulated in concert in certain conditions or disease states (e.g., infection, autoimmunity, etc.) will be performed. Data will be used to compare the baseline with responses post-treatment. Additionally, joint models of overall survival and longitudinal biomarkers may be explored.

10.2.2.6.5 Tumor Growth Rate, Progression Arrest Rate, Clinical Benefit Rate, and Quality of Life

Tumor growth rate and PAR will be explored between treatment arms. Additionally, the relationship between TGR and OS, and PAR and OS, may be explored.

Clinical benefit rate will be explored using methods similar to that described for ORR.

Quality of life as a composite endpoint (including but not limited to the following: while on study, the incidence of hospitalization, transfusions, and laboratory markers [eg. absolute neutrophil count, hemoglobin, and platelets]) will be explored.

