# 7.6.2.2 Immune response and histologic and molecular tissue changes in tumor tissue or peripheral blood

Baseline and post treatment anti-NY-ESO-1 immune response and histologic and molecular changes in peripheral blood and tumor tissue and their association with clinical outcomes will be explored. Pre and post dosing antibody and T cell (+ vs -) will be summarized. In addition, a relationship between an induced anti-NY-ESO-1 immune response as well as tumor tissue changes during study treatment and clinical outcomes will be evaluated using peripheral blood and tumor tissue biopsies collected during study treatment at select sites. Association between Pre and post dosing antibody and T cell (+ vs -) and clinical outcome (PFS, OS) will be explored. Stepwise Cox regression analysis will be explored to investigator prognostic baseline factors associated with clinical outcome (OS, PFS).

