# 7.9 Multiplicity

Where possible, parameters will be quantified for direct comparisons between the treatment arms. Since the sample size is not based upon a hypothesis to be tested regarding the differences in primary and secondary endpoints between treatment arms, the statistical analyses to compare differences in parameters between treatment arms should be considered exploratory. All other statistical tests (where performed) will be two-sided and tested at the alpha=0.05 level of significance; all these p-values produced should be deemed descriptive. There will be no adjustment to multiplicity.

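### Immunogenicity is to be compared between arms, but the only significance test stated is change from baseline, and no estimate or interval for the arm difference is planned

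*Protocol*

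**What the plan says.** Protocol 4.1.3 states a comparative aim: "To evaluate the immunogenicity of CMB305 in combination with atezolizumab compared to atezolizumab alone". SAP 2.3 repeats it.

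The method is in Protocol 10.2.2.6.3, and the synopsis repeats it. For T cells: "Descriptive statistics will be performed comparing the baseline and treatment administration peripheral blood NY-ESO-1-responsive T cells between the 2 treatment arms". The next sentence carries the only inference: "Analyses will be performed to determine if there are any statistically significant changes from baseline values". It names no arm, statistic or time point. For antibodies: "Changes from baseline in serial anti-NY-ESO-1 antibodies will be expressed as geometric mean titers", with no contrast between arms.

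SAP 7.6.2.2 states "Pre and post dosing antibody and T cell (+ vs -) will be summarized" and then turns to associations with PFS and OS. It names no test or interval for the difference between arms. It also contains no change-from-baseline test. SAP section 8 lets the SAP prevail where the two documents differ.

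Three further statements bear on the point. Protocol 10.2.2.4.2 and SAP 7.1 provide summaries by treatment arm. SAP 7.9 says "Where possible, parameters will be quantified for direct comparisons between the treatment arms". For gene biomarkers, Protocol 10.2.2.6.4 says "treatments will be compared using analysis of variance (ANOVA), or non-parametric method when appropriate, of specific genes".

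**The concern.** The null hypothesis of a change-from-baseline test is that nothing changed over time. The objective needs a different null: that adding CMB305 to atezolizumab makes no difference. The two part company whenever something moves the assay in both arms, such as atezolizumab itself, time, or regression to the mean. Protocol section 3.0 gives a reason to expect such movement. It hypothesizes that tumor-reactive T cells are present but suppressed, and that blocking the PD-1/PD-L1 axis restores their activity.

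At stake is the interpretation of the immune data, where the mechanism of CMB305 is examined. A p-value would be attached to a contrast that does not answer the question, while the contrast that does would have neither an estimate nor an interval. Other exploratory endpoints do have a between-arm method: stratified log-rank tests for OS, PFS and DOR, logistic regression for ORR, and ANOVA for genes.

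**Working it through.** **No figure to reproduce.** The documents give no effect size, SD or power for immunogenicity. What follows is an illustration.

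**Inputs from the documents**
- About 40 patients per arm, randomized 1:1 and stratified by disease type (Protocol 5.1 and 10.3.1).
- Two-sided tests at 0.05: "All other statistical tests (where performed) will be two-sided and tested at the alpha=0.05 level of significance".
- Both arms sampled at baseline and on Days 42, 70 and 98 (schedules of events), but only at sites trained in PBMC isolation, so the number with data may be below 40. I also show 20.

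**Assumptions**
- Both arms rise by the same 0.3 SD and CMB305 adds nothing.
- The pre/post correlation ρ is 0.5.

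**Step 1: change-from-baseline test in the combination arm.**
- SD of change = σ√(2(1 − ρ)) = σ√(2 × 0.5) = σ, so the standardized change is d = 0.3.
- Noncentrality = d√n = 0.3 × √40 = 1.90. The noncentral t with 39 degrees of freedom gives a probability of significance of 0.457, about 46%.
- At 20 per arm: 0.3 × √20 = 1.34, probability 0.247.

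Over other assumed shared changes:

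| n per arm | d = 0.2 | d = 0.3 | d = 0.5 | d = 0.8 |
|---|---|---|---|---|
| 40 | 0.235 | 0.457 | 0.869 | 0.999 |
| 20 | 0.136 | 0.247 | 0.565 | 0.924 |

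**Step 2: between-arm test, same setting.** The shared rise cancels, so the rejection rate stays near 0.05. In 20,000 simulated trials, ANCOVA on the baseline value rejected in 4.9% at 40 per arm and 5.0% at 20.

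**Step 3: a real effect on top of a shared one.** Let both arms rise 0.5 SD and CMB305 add a further 0.5 SD, with 40 per arm. Simulation gives both within-arm tests significant in 87% of trials, which leaves the added effect unidentified. ANCOVA has 72% power to detect it.

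**Step 4: precision available.**
- ANCOVA residual SD = σ√(1 − ρ²) = σ√0.75 = 0.866σ. The 95% CI half-width for the arm difference at one visit is about 1.96 × 0.866 × √(2/40) = 0.38 SD at 40 per arm, and 1.96 × 0.866 × √(2/20) = 0.54 SD at 20.
- For responder proportions near 50%, the half-width is about 1.96 × √(2 × 0.25/40) = 0.22 at 40 per arm, and 1.96 × √(2 × 0.25/20) = 0.31 at 20.

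**Step 5: why not rest on Day 98 alone.** Day 98 is 98/30.4375 = 3.22 months. With exponential PFS and the plan's medians of 3 and 5.2 months, the fraction progressed or dead by then is 1 − 0.5^(3.22/3) = 52% or 1 − 0.5^(3.22/5.2) = 35%. Some patients may stay on treatment after progression, so sample loss is unknown, but a model that uses all post-dose days is safer.

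**The case against.** The case against has real force on four points.

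1. **The control arm is used.** A reader might infer that the randomized control plays no part in the immune analysis. The documents do not support that: T cells are compared descriptively between arms and summaries are by arm, so a shared change would appear side by side. What is missing is an estimate or interval for the difference.

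2. **No rule credits CMB305 for significance in one arm only.** A reader might infer that the sponsor will claim an effect if the combination arm alone is significant. Under the assumptions of Step 1 that pattern has probability 0.457 × (1 − 0.457) = 0.248 at 40 per arm, but no such rule appears in either document. The sentence on change from baseline does not even say which arm it covers.

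3. **The 46% is not an error rate of the stated test.** A true rise is built in, and the test correctly detects it. The figure becomes misleading only if the result is read as an effect of CMB305.

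4. **The stakes are limited.** The comparative objective is exploratory, p-values are nominal, and no decision rule uses immunogenicity. The rule for recommending further study uses the 6-month progression-free rate.

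Two other replies do not hold. The general line in SAP 7.9 names no test, scale or time point for immunogenicity. The ANOVA in Protocol 10.2.2.6.4 is for gene biomarkers, not for the T-cell and antibody measures of 10.2.2.6.3.

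**Conclusion.** The point holds in a limited form. The question is comparative, and the one inferential statement for T-cell and antibody immunogenicity addresses change over time. Neither document plans an estimate or interval for the arm difference. By-arm summaries reduce the risk of misreading but do not quantify the difference or its uncertainty.

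In the main illustration a significant change in the combination arm arises in about 46% of trials with no CMB305 contribution, against about 5% for a between-arm ANCOVA. These figures rest on an assumed shared rise of 0.3 SD, a correlation of 0.5 and data from 40 patients per arm, none of which the documents give for immunogenicity. They show how the two contrasts differ and do not predict this trial. Because the analysis is exploratory with nominal p-values, this should be corrected but does not threaten the trial's main conclusions.

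**What to change.** In Protocol 10.2.2.6.3, make the inferential analysis a comparison between arms. Add the same to SAP 7.6.2.2, which has no test to replace and would otherwise prevail without one.

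- **Quantitative T-cell and antibody values:** model the log post-dose value in one repeated-measures model with all post-dose samples (Days 42, 70 and 98), adjusted for log baseline and disease type. Report the arm ratio with 95% CI. State which baseline draw is used, since two are taken, and how values at or below the assay limit enter the log scale.
- **Positive/negative status:** report the between-arm difference in post-dose responder proportions with 95% CI.
- **Within-arm changes:** keep as description, without p-values.
- **Label:** call the comparison exploratory.

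The change should be made before immune data are compared by arm. It costs SAP wording and minor programming, with no new samples. The drawback is modest precision, because blood comes only from sites trained in PBMC isolation.
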